Study Protocol and Statistical Analysis Plan

Effect of Hearing Aid Labeling on Speech Understanding Measures

Version 1.0

05/23/2022

NCT05274178

Protocol Title

Effect of Hearing Aid Labeling on Speech Understanding Measures

1 Background

The purpose of this study is to investigate the placebo effect of labeling hearing aids as "OTC" (over-the-counter) or "Prescriptive" for inexperienced and experienced hearing aid users with mild to moderate hearing loss.

Previous interest in placebo effects for hearing aid research have centered around labeling devices as "digital" vs. "conventional" (Bentler et al. 2003) and "new" vs. "old" (Dawes et al. 2011, 2013). These studies found that participants had strong preferences for devices labeled as "digital" and "new" even when all variables between conditions were equal besides the label. In addition to the effect of labeling, Rakita et al. (2021) have shown that end users are also susceptible to placebo effects stemming from the language used by the hearing aid fitter. Specifically, it was found that when the participants were given a positive narrative for hearing aid expectations, they performed better in behavioral measurements (i.e. lower SNRs via the QuickSIN) and anticipated needing less time to get used to the hearing aids as compared to a negative narrative. These findings have shown that placebo effects are measurable in hearing aid research and do have an impact not only on device preference but also hearing performance.

The recent release of FDA guidelines for OTC hearing aids has created an urgency to understand the impact of these devices on the hearing aid market. Device labeling has been proven to influence consumer preference in hearing aid research, but the specific effect of labeling devices as "OTC" or "Prescriptive" has not been previously investigated; therefore, it is worthwhile for Sonova to pursue this investigation in order to understand the impact of OTC labeling on consumer behavior and perceptions.

2 Objectives

The primary objective is to investigate the effect of hearing aid labeling on objectively measured speech understanding in noise for inexperienced and experienced hearing aid users with mild to moderate hearing loss.

3 Description of the investigational device

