There are minimal risks associated with both the investigational device and participating in the clinical investigation. Identified risks are no greater than those associated with the daily use and wear of approved, available hearing aids. The device used presents non-significant risk per FDA.

The benefits of participating in the investigation include the possibility of hearing sounds that have not been previously heard, such as speech and environmental sounds, which may improve communication in daily life. Subjects may experience the benefit of personal satisfaction for participating in research to improve hearing instrument technology. Subjects will also be compensated for their time in participating in this study.

There are no known or anticipated risks to subject hearing ability associated with participation in this study. All sounds used in this study will be presented at safe listening levels. While using hearing aids, the following are possible occurrences:

- Cerumen impaction
- Ear discomfort, pain or soreness
- Sweat or moisture accumulation in the ear canal or pinna
- A feeling of pressure or fullness in the ear
- Itching, blisters, or sores in the ear canal or pinna
- Headache
- Redness of tissue

The research personnel will review these risks with the subjects and answer any questions they have. Hearing aids are not a significant risk investigational device as defined in the FDA 21 CFR 812.3(m).

6 Endpoints

Primary endpoint:

- Quick Speech-in-Noise (QuickSiN) benefit score. QuickSiN is an adaptive test of an individual's ability to understand speech in noise. The test adapts the relative levels of noise and speech to determine the signal-to-noise ratio (SNR) at which the individual can correctly identify 50% of key words. This test was independently developed and validated and is available for use by clinicians and researchers (Killion, et al., 2004).

7 Inclusion and Exclusion Criteria

Subjects fulfilling all of the following inclusion criteria are eligible for the investigation:

- Adults and adolescents 18-95 years of age
- Target recruitment is for 15 first-time hearing aid users and 15 experienced hearing aid users
- Mild to moderate (N1-N3) bilateral hearing loss
- Fluent in English; ability to read and write in English
- Willing and able to provide informed consent

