Participants must meet the eligibility criteria for OTC hearing aids per the FDA. New-to-hearing aid participants must not have prior hearing aid experience, defined as never owning their own devices. Experienced hearing aid participants must have at least 6 months of hearing aid use with their own devices

The presence of any one of the following exclusion criteria will lead to the exclusion of the subject:

- Self-reported ear-related pathology (otorrhea w/in 90 days, dizziness, sudden hearing loss or worsening of hearing w/in 90 days, otalgia)
- Visible deformity of the ear
- Chronic, severe tinnitus
- Unilateral hearing loss
- Cognitive impairment

8 Measurements and procedures

15 inexperienced users and 15 experienced hearing aids users will be recruited for this study. They will be told they are participating in a research study comparing two sets of hearing aids. One set of hearing aids will be labeled as "OTC" devices, while the other will be labeled as "Prescriptive" devices. Definitions for OTC hearing aids and prescriptive hearing aids will be provided to the participants verbally; however, all the participants will see are two identical hard shell hearing aid cases with a physical label on them that say "OTC" and "Prescriptive." The participants will complete the QuickSiN for both conditions (OTC and prescriptive) in order to assess if there is a labeling effect on objective speech understanding performance in noise.

Data will be captured at the time of testing. Data will be stored electronically on a Sonova-owned server and will be analyzed after all participants have completed all investigation tasks and appointments. Any computing code generated to conduct the analysis will be stored with the data following the analysis.

There will be two researchers involved in this study. One researcher will speak with the participants, place the hearing aids in their ears, and administer the questionnaires. The other researcher will score the objective testing while blinded to the condition.

9 Statistical design and analysis

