An a priori power analysis was conducted in G*Power3 for the primary objective. The primary objective will be measured for two groups (experienced and inexperienced) via repeated measures of the QuickSiN for two conditions (OTC and prescriptive). A repeated measures, within and between factors ANOVA, using a medium effect size ($f = .55$) and alpha of .05, would require a sample of 14 participants per group (inexperienced and experienced) for a total of 28 participants to achieve a power of .95.

Speech-in-noise (i.e. QuickSiN) data for the primary objective from all subjects will be analyzed. Participants will be grouped by hearing aid experience (either inexperienced or experienced) as a part of these analyses. For the primary objective and its associated endpoint (QuickSiN benefit), two lists will be presented for each condition in order to expect a 1.8 dB critical difference between the conditions with a 80% confidence level. The principal investigator will conduct the analysis of the primary endpoint after data has been collected from all participants for all test conditions.

10 Investigation Duration

This investigation is scheduled to last approximately 10 weeks. Each participant's duration will be one day of testing.

11 Data handling and management

Electronic or paper based CRFs will be used to capture the participant data. If electronic, subjective questionnaires will be available in the EDC system and the participant will be able to read question and choose answer. If paper based subjective questionnaires are used, the participant will answer each question and the results will be transferred to the EDC by the investigator. Objective data will either be entered in directly to the EDC system, or transferred from a paper based CRF into the EDC system.

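### Section 9 calls f = .55 a medium effect, and the printed inputs do not give 28 participants for the label effect, so .95 power for a medium effect is not supported

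*Combined protocol and SAP*

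**What the plan says.** Section 9 of the combined protocol and SAP opens: "An a priori power analysis was conducted in G*Power3 for the primary objective". Section 2 defines that objective: "The primary objective is to investigate the effect of hearing aid labeling on objectively measured speech understanding in noise". The label is compared within each participant, since section 8 has everyone complete the test under both labels.

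The stated inputs are two experience groups, two label conditions, alpha .05, power .95 and an ANOVA "using a medium effect size ($f = .55"). The stated result is that this "would require a sample of 14 participants per group (inexperienced and experienced) for a total of 28 participants to achieve a power of .95".

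Section 9 does not say which ANOVA effect was powered (label, experience, or their interaction), which scale f is on, or what correlation between the two conditions was assumed. No section gives an SD or an expected difference in dB from which f was derived. Recruitment is set slightly above the requirement, at 15 per group, in section 7 ("Target recruitment is for 15 first-time hearing aid users and 15 experienced hearing aid users") and again in section 8.

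**The concern.** Two things do not fit.

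- **The word and the number disagree.** On the usual convention for f, medium is .25 and large is .40. The convention is not in the documents and is taken here as an assumption. A value of .55 is more than twice medium.
- **The number does not lead to the total.** For a within-person comparison, f = .55 should need fewer than 28 people unless the two conditions are negatively correlated.

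Section 9 is the plan's only statement of what the trial can detect on its only listed endpoint. A reader of a null label result would take from it that the trial had .95 power against a medium effect. Whether it did depends on a correlation that the plan does not state.

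**Working it through.** **Inputs.** From section 9: 2 groups, 2 conditions, f = .55, alpha .05, target power .95, N = 28. From sections 7 and 8: planned N = 15 + 15 = 30. Assumed, because the plan gives none: the correlation ρ between a participant's two condition scores, shown over a range.

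**Size of f.** For a two-level main effect with equal numbers, d = 2f. So f = .55 is 2 × .55 = 1.10 SD, and f = .25 is 0.50 SD.

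**Formula.** Power comes from the noncentral F distribution with 1 and N − 2 degrees of freedom. For the label effect, and equally for the label-by-experience interaction, the noncentrality is λ = 2f²N/(1 − ρ).

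**Step 1: try to reproduce 28 at f = .55.** With f² = .3025 and N = 28, λ = 2 × .3025 × 28/(1 − ρ) = 16.94/(1 − ρ).

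| ρ (assumed) | λ at N = 28 | Power at N = 28 | Smallest even total for .95 |
|---|---|---|---|
| 0 | 16.94 | .977 | 24 |
| .3 | 24.20 | .997 | 18 |
| .5 | 33.88 | .9999 | 14 |

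The required total falls as ρ rises, so it is at most 24 for any ρ of 0 or above. A total of 28 would need ρ of about −.12 to −.20, which is hard to credit for two scores from one listener on one day.

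**Step 2: the other scale for f.** If f already includes the correlation, ρ drops out.

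- With λ = f²(N − 2) = .3025 × 26 = 7.87, power at 28 is .77 and 48 are needed.
- With λ = f²N = .3025 × 28 = 8.47, power at 28 is .80 and 46 are needed.

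Neither gives 28.

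**Step 3: take the word medium at face value.** With f = .25, f² = .0625, so λ = 3.5/(1 − ρ) at N = 28 and 3.75/(1 − ρ) at N = 30.

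| ρ (assumed) | Power, N = 28 | Power, N = 30 |
|---|---|---|
| 0 | .44 | .46 |
| .3 | .58 | .61 |
| .5 | .72 | .75 |
| .7 | .91 | .93 |
| .8 | .98 | .99 |

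Power reaches .95 at ρ = .751 with 28 participants and at ρ = .731 with 30.

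**Step 4: can 28 arise some other way?** Yes, in set-ups other than a label effect in a 2 × 2 design.

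- *Experience main effect.* With λ = 2f²N/(1 + ρ), f = .55 and ρ = .2, λ = 16.94/1.2 = 14.12. Power is .951 at N = 28 and .935 at N = 26.
- *Interaction with four between-subject cells (experience by order).* With 3 and N − 4 degrees of freedom, 28 is the answer at ρ of about .18 to .30. Power at 28 is .954 at ρ = .18 and .978 at ρ = .30; at ρ = .30, N = 24 gives .948.
- *Three measurements, with f including the correlation.* With λ = 2f²N, N = 28 gives .956 and N = 26 gives .941.

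The first is not the primary objective. The other two depart from the two groups and two conditions that section 9 describes.

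**The case against.** **The trial has enough participants for the printed f.** This stands on the standard scale: label power is at least .977 with 28 at any ρ of 0 or above, and 30 are planned. A reader might infer from the mismatch that the trial is too small for its stated effect. On that scale the documents do not support this; only the alternative scale would put power at 28 as low as .77 to .80.

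**Medium is only an adjective, judged by an outside convention.** This stands in part. The operative input is .55, and nothing shows that .25 was intended. The zero-correlation figure of .44 is also a pessimistic extreme for repeated scores on one day. But the failure to obtain 28 does not depend on the adjective, and the adjective is what a reader would carry into the interpretation of a null result.

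**Some other calculation may lie behind 28.** This stands, and it limits what can be said. One might infer that only the experience main effect gives 28, but that is true only for two groups and two measurements. One might also infer that a total of 14 (the answer at ρ = .5) was misread as 14 per group. That needs a correlation the plan never states, and section 9 gives its per-group and total figures consistently. A third guess is that .55 was a standardised mean difference, so that f = .275; then 28 gives .80 at ρ = .5 and needs ρ of about .70 for .95. The documents confirm none of these.

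**Conclusion.** The sentence in section 9 is wrong as written. In the design it describes, f = .55 calls for at most 24 participants for the label effect on the standard scale (ρ of 0 or above), or 46 to 48 on the alternative scale, but not 28. If a medium effect of f = .25 was meant, .95 power with 28 holds only at ρ of about .75 or more. Over assumed ρ of 0 to .7, power runs from .44 to .91.

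This rests on two measurements per person, a non-directional test at alpha .05, the usual convention for f, and a ρ that the plan does not supply. The documents do not show whether the word, the value of f, the total or the unstated settings are at fault. The consequence is confined to the stated sensitivity and to how a null label result would be read.

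**What to change.** Check the saved G*Power settings, then replace the sentence in section 9 with one of this form:

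> The effect powered is the label main effect, with f = [value] on the [named] scale, based on [expected difference in dB and SD]. The assumed correlation between conditions is [value] and alpha is .05. The required total is [value], and power with the planned 30 participants is [value].

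If the saved run powered a different effect, say so and give the figure for the label effect as well. If f = .55 stands, remove the word medium and give the reason for expecting an effect of that size. If it does not stand, correct f and recompute. In either case, do not claim .95 power for a medium effect unless the stated correlation supports it (about .73 or more with 30 participants at f = .25).

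The cost is a check of saved settings and two or three sentences. No participants are added and no procedure changes. The downside is a less favourable stated power for a medium effect.

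### Section 9's pairing of 28 participants with power .95 at f = .55 is not reproduced for the label test it is said to support; the cause and direction of the mismatch are not established

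*Combined protocol and SAP*

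**What the plan says.** Section 9 states: "An a priori power analysis was conducted in G*Power3 for the primary objective". It describes the design as follows: "The primary objective will be measured for two groups (experienced and inexperienced) via repeated measures of the QuickSiN for two conditions (OTC and prescriptive". The method is "A repeated measures, within and between factors ANOVA", "using a medium effect size ($f = .55$) and alpha of .05", and the result is that this "would require a sample of 14 participants per group (inexperienced and experienced) for a total of 28 participants to achieve a power of .95".

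Section 2 defines what is to be powered: "The primary objective is to investigate the effect of hearing aid labeling on objectively measured speech understanding in noise". Section 8 says the QuickSIN is completed under both labels "in order to assess if there is a labeling effect on objective speech understanding performance in noise". Section 8 also sets recruitment slightly above the calculated number: "15 inexperienced users and 15 experienced hearing aids users will be recruited for this study".

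Three inputs to the calculation are not given anywhere: which of the three F tests was powered (label, experience, or their interaction), the correlation assumed between the two conditions, and the scale on which f is expressed.

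**The concern.** The primary objective is a contrast between labels within the same person. In a two-by-two mixed ANOVA, the label effect and the label-by-experience interaction are both tested on 1 and N - 2 degrees of freedom. With f, alpha and N fixed by Section 9, power depends only on the effect-size scale and, on one scale, on the correlation. It is therefore possible to check whether any plausible choice gives 28 and .95 for the test that matters. None does.

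This is the plan's only sample-size justification, and it concerns the only stated endpoint. If the label effect turns out not to be significant, a reader will take it that an effect of f = .55 would have been missed 5% of the time. Depending on the unstated inputs, the type II error at 28 could be about .23, .20, .023 or below .001.

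**Working it through.** **Inputs.** From Section 9: two groups, two conditions, f = .55 (f² = .3025), alpha .05, N = 28 (14 per group), stated power .95. Assumed, because the plan does not state them: rho between conditions, taken from 0 to .7, and the scale of f, with each option tried. Power is the upper tail of the noncentral F beyond the central 5% point. Required totals are the smallest even N (equal groups) reaching .95.

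**1. Label effect or label by experience, f excludes rho.** λ = 2f²N/(1 - rho), df 1 and N - 2. At N = 28 and rho = 0, λ = 2 × .3025 × 28 = 16.94, and power is .977. A simulation of this case with 100,000 runs also gave .977.

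| rho | Power at 28 | Required total |
|---|---|---|
| 0 | .977 | 24 (22 gives .934, 24 gives .953) |
| .2 | .993 | 20 |
| .3 | .997 | 18 |
| .5 | .9999 | 14 |
| .7 | above .9999 | 10 |

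A required total of 28 appears only for rho between about -.20 and -.12. Negative correlation between two scores on the same test, from the same person on the same day, would be hard to defend.

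**2. Same tests, f absorbs rho.** The correlation then drops out.
- λ = f²N: at 28, λ = .3025 × 28 = 8.47 and power is .800. At 44 it is .946 and at 46 it is .954, so 46 are required. At the planned 30, power is .828.
- λ = f²(N - 2): at 28, λ = .3025 × 26 = 7.865 and power is .770. At 46 it is .946 and at 48 it is .955, so 48 are required. At 30, power is .802.

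**3. Where the stated pair does appear.**
- Experience (between-group) main effect: λ = 2f²N/(1 + rho), df 1 and N - 2. At rho = .2, λ = 16.94/1.2 = 14.12 and power at 28 is .951. The required total is 28 for rho of about .12 to .20. At rho = .5, power at 28 is .899 and 36 are required.
- An interaction across four cells (3 and N - 4 df) gives .958 at 28 with rho .2, and .978 with rho .3. Section 9 specifies two groups of 14, so this does not fit its description.

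**4. A figure that needs neither rho nor scale.** Express the label main effect as the mean within-person difference divided by the SD of that difference (dz). Then λ = N·dz², df 1 and 26 at N = 28.
- Power .95 needs λ = 14.04, so dz = √(14.04/28) = 0.71.
- Power .80 needs λ = 8.47, so dz = √(8.47/28) = 0.55.

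**The case against.** The best reply is that the calculation may be sound and only poorly described. If f excludes the correlation, 28 does deliver more than .95 for the label test at every non-negative rho, and the only thing wrong is the claim that 28 are required. If the planners sized the trial on the most demanding of the three F tests, 28 and .95 is right for the experience effect at rho of about .12 to .20, and the label test would then have about .99 power. Section 4 also randomizes order within each experience group, which makes four cells and gives the four-cell reading some basis.

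Much of this stands. It rules out saying that the calculation is wrong in a known direction. It does not rescue the sentence as written, because Section 9 attributes the calculation to the primary objective, which is labeling, and does not say that N was set by another test. Its wording of 14 per group also points to two groups rather than four.

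Two stronger readings are tempting, and neither is supported. A reader might infer that the trial is underpowered. That follows only if f absorbs the correlation, and nothing in Section 9 says that scale was used. A reader might also infer that the detectable label effect is unknowable from the plan. It is not: in SD units of the within-person difference it follows from N, alpha and the design (step 4). What cannot be recovered is the effect in dB that the planners had in mind, because Section 9 gives no SD for the difference.

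**Conclusion.** The finding holds as a mismatch between the stated pair and the stated objective. For the label effect or label by experience at f = .55 and alpha .05, no non-negative correlation on the scales examined gives a required total of 28 for .95 power. The required total is 24 or fewer (power at 28 at least .977), or 46 or 48 (power at 28 of .80 or .77). The result rests on the two-group, two-condition design in Section 9, on equal groups, and on the assumed range of rho and choice of scale, which the plan does not give.

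Which unstated input produced 28 is not established, and nor is whether the stated power is too high or too low. The point should be fixed because it affects how a null result will be read. It gives no reason to change enrollment.

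**What to change.** Keep enrollment at 15 + 15. Replace the power sentence in Section 9 with a figure for the label test, for example:

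> With 28 completers (14 per group), the label main effect (F, 1 and 26 df, alpha .05) has .95 power for a mean OTC-prescriptive difference of 0.71 SD of the within-person difference, and .80 power for 0.55 SD.

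The sponsor should add the SD it assumes for that difference, in dB, so that the detectable effect can be read on the QuickSIN scale.

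If f = .55 is kept, name the F test, the effect-size option and rho, taken from the original power output or from a rerun, and state the N and power that match. If 28 was set by the experience effect, say so and add the label-effect figure beside it.

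The cost is one revised sentence and one check or rerun of the calculation. No participants or procedures are added.

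### Does leaving the deciding ANOVA term unnamed in Section 9 inflate the chance of a false label finding?

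*Combined protocol and SAP*

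**What the plan says.** Section 2 (Objectives) gives one primary objective: "the effect of hearing aid labeling on objectively measured speech understanding in noise for inexperienced and experienced hearing aid users". Section 8 describes the QuickSiN comparison as a check for a labeling effect on speech understanding in noise. Section 6 names the endpoint as "Quick Speech-in-Noise (QuickSiN) benefit score" and gives no formula for benefit.

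Section 9 names the model only in its sample-size sentence: "A repeated measures, within and between factors ANOVA, using a medium effect size", with f = .55, a single alpha of .05 and power of .95, which "would require a sample of 14 participants per group (inexperienced and experienced) for a total of 28 participants". On the analysis itself it says "Speech-in-noise (i.e. QuickSiN) data for the primary objective from all subjects will be analyzed" and "Participants will be grouped by hearing aid experience (either inexperienced or experienced) as a part of these analyses". It names no deciding term, testing order or multiplicity rule. The recruitment target is 15 per group, 30 in all (Sections 7 and 8).

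**The concern.** The named ANOVA has two terms that involve the label: condition, and condition by experience. The objective mentions both user groups, so either term could be presented as the answer, and so could a label test within each group. If whichever term is significant can be reported as a label effect, the error rate is no longer 5%. The terms can also disagree. When the label affects one group only, one term is often significant without the other, and the plan does not say which result stands. The principal investigator runs the analysis after all data are in, so a choice left open until then could be shaped by the results.

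The sample-size sentence might have settled the matter by showing which term was powered. It does not, because neither the term nor the correlation between conditions is stated.

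**Working it through.** **Inputs.** From the plan: two groups, two conditions, alpha .05, f = .55, power .95, 28 participants required, 15 + 15 recruited. Not in the plan, so varied or assumed: the correlation ρ between a participant's two condition scores, and the label effect d in units of the SD of the paired differences.

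**1. The plan's own figure.** With f relative to the single-condition SD and N participants in total, both label terms have noncentrality λ = f²·N·2/(1 − ρ) and the experience term has λ = f²·N·2/(1 + ρ). Each is an F test on 1 and N − 2 df. At N = 28 and ρ = 0, λ = 0.3025 × 28 × 2 = 16.94, and power is .977.

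| ρ | Smallest even N, label terms | Smallest even N, experience term |
|---|---|---|
| 0 | 24 | 24 |
| .2 | 20 | 28 |
| .5 | 14 | 36 |

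A total of 28 is not the required size for a label term at any ρ of 0 or above. It matches the experience term near ρ = .2, and 14 matches a label term at ρ = .5, which is the number the plan gives per group. Either match could be chance. If f came from partial eta-squared, λ = f²·(N − 2) and a label term would need 48. The figure therefore does not reveal the intended term.

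**2. Error rate with no label effect, 15 + 15.** The two label terms have independent numerators and share one error mean square on 28 df. With t = 2.048 (two-sided .05),

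P(at least one significant) = 1 − ∫ [2Φ(t·√(s/28)) − 1]² · g(s) ds, where g is the chi-square density on 28 df.

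This gives 9.65%. A simulation of 1,000,000 trials gave 9.68%. For comparison, two fully independent tests give 1 − .95² = 9.75%. If the condition term alone decides, the rate is 5.0%.

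**3. What a testing order would cost.** Let d₁ and d₂ be the label effects in the two groups. The condition term has λ = 30·((d₁ + d₂)/2)², the interaction λ = 30·((d₁ − d₂)/2)², both on 1 and 28 df. A joint test of both group effects has λ = 15·(d₁² + d₂²) on 2 and 28 df.

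| Assumed d₁, d₂ | Condition | Interaction | Either term, no order | Joint 2-df test |
|---|---|---|---|---|
| 0.5, 0.5 | 75% | 5% | 76% | 64% |
| 0.5, 0 | 26% | 26% | 45% | 36% |
| 0.7, 0 | 46% | 46% | 69% | 63% |
| 0.5, −0.5 | 5% | 75% | 76% | 64% |

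For 0.7, 0: λ = 30 × 0.35² = 3.675 for each term. Exactly one of the two is significant in 2 × 69.4% − 2 × 45.7% = 47% of trials. Making the condition term a gate lowers the chance of any label finding from 69% to 46%. With opposite effects the gate opens in only 5% of trials, although the interaction alone has 75% power.

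**4. The undefined benefit score.** If benefit means an unaided score U minus the aided score, with one U per participant, the label contrast is (U − Prescriptive) − (U − OTC) = OTC − Prescriptive. U cancels. If benefit means the difference between conditions, the contrast is the same up to sign. Both label tests therefore come out the same under these definitions.

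**The case for a change.** The best case for a change is that this combined document is the SAP, and a lean towards one term is not pre-specification. One sentence naming the condition term would remove the 9.6% reading. A fixed order with the condition term first does hold the error at 5%: the four null hypotheses (condition, interaction, and each group) constrain two group effects, so if any two are true, all four are. Section 12 provides a route for amendments.

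The gap in wording and the arithmetic both stand. A sentence stating the primary term and the role of the interaction would be good practice, as would a definition of benefit. What does not stand is the step from silence to a doubled error rate: that needs a decision rule found nowhere in the plan. Nor is an order costless, as step 3 shows. Choosing between a condition gate, a joint test and separate tests depends on whether an effect in one user group alone should count, and statisticians would reasonably differ on that.

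The 1.8 dB figure adds nothing here. Section 9 offers it as the reason for the amount of testing ("two lists will be presented for each condition in order to expect a 1.8 dB critical difference between the conditions"), and no count of participants beyond it is planned.

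**Conclusion.** No change follows. Section 9 is sparse, but the model is named, the factors are clear, and the objective is a label effect. An analyst would read the condition term as that effect and the interaction as whether it differs by experience, each at its own .05. On that reading the false-positive rate for the primary question is 5%. The 9.6% arises only if either significant term would be reported as the label effect, which the documents neither state nor exclude.

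An imposed order would exchange that conditional excess of about 4.6 percentage points (9.6 − 5.0) for lower power where the groups differ: 46% against 69% at 0.7 SD in one group. These power figures assume normal paired differences with equal variance in the groups and effect sizes that the plan does not give. The required total of 28 cannot be reproduced for a label term without knowing the correlation and the definition of f. That leaves its basis incompletely stated; it does not show that 28 is too few.
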